6.7 Study Calendar

	Pre-Enrollment Period	Study Day 0 (Day of Extubation)	Study Day 1	Study Day 2	End of Study
Patient Identification and pre-screening	X				
Recruitment/informed consent	X				
Spontaneous Breathing Trial	X	X			
Eligibility Verification		X			
Enrollment		X			
NIV/HFNC Protocol		X	X		
Postextubation Management Worksheet		X	X	X	
30-Days following Discharge					X

6.8 Study Limitations

A potential limitation of this study is that participants for whom informed consent is obtained may not be representative of the population as a whole, which would limit the generalizability of the data. The extent to which demographics of those enrolled differ from the population as a whole will be assessed as outlined in [Section 7.1](#).

7 Data Collection, Handling & Record Keeping

With the exception of source data recorded using the Postextubation Management Worksheet (Appendix G), all study data will be recorded directly from electronic medical records into the study-specific REDCap database (Appendix A for prospective cohort data and Appendix F for historical control cohort). Research Electronic Data Capture (REDCap) is a secure web application for building and managing online surveys and databases. The REDCap program and the resulting data are maintained on internal servers and backed up regularly. REDCap has the technical capabilities to be HIPAA and 21 CFR 11 compliant.

The Postextubation Management Worksheet will be maintained at the patient's bedside until completed, at which point the data will be entered into REDCap and the paper files will be given to OhioHealth Research Institute.

The data collection and storage processes will follow HIPAA guidelines and OhioHealth policy to protect both confidentiality and privacy of each participant. Paper files will be stored in a secure facility with limited access (e.g., the offices of the OhioHealth Research Institute) and electronic files will be stored within the OhioHealth network, under password protection and encryption. All PHI data will be destroyed at the end of the study and only de-identified data will be maintained.

Per Health and Human Services Federal Regulations, research-related documents will be maintained for at least three years after completion of the research. All research-related documents (e.g., informed consent forms, data collection forms, electronic spreadsheets) will be provided to OHRI for retention.

7.1 Statistical Analysis Plan

In general, categorical variables will be summarized with counts and percentages; and continuous variables will be summarized with means, standard deviations, medians and ranges. The two groups will be compared on categorical variables using chi-square tests, or Fisher's exact tests if the data in the contingency table have cells with expected frequency of $n < 5$. The two groups will be compared on the continuous variables using a t-test if the variable is approximately normally distributed or using a Wilcoxon rank sum test if the variable is markedly non-normally distributed. These general statistical methods will be used to compare groups on all the demographics and baseline characteristics, for the intention to treat (ITT) and per protocol (PP) populations.

Results will be considered statistically significant if the p-value is less than or equal to 0.05. SAS V9.3 or higher will be used for all summary statistics and statistical analyses.

7.1.1 Primary Statistical Analysis Methods

Because this is a non-randomized study, it is assumed that there will be some differences between groups on the demographics and/or baseline characteristics. Therefore logistic regression modeling

techniques will be used for the primary statistical analyses. This will allow for comparison of the groups on reintubation rate while adjusting out baseline differences.

The primary analysis is comparison of the groups on reintubation rates within 72 hours on the ITT population. Potential differences between groups on demographic and baseline characteristics will be adjusted for in the model by including any statistically significant demographic and baseline characteristics as covariates in the logistic regression model.

Additional primary analyses include:

Re-intubation required (no/yes)

- a. Within 24 hours
- b. From 24-48 hours
- c. From 48-72 hours
- d. >72 hours but ≤ 7 days

The same methods used for the primary analyses will be repeated for these additional primary outcomes (within 24, 24-48, 48-72, and >72hrs) for the ITT population; and these analyses will also be repeated for the PP population (within 24, 24-48, 48-72, and >72hrs).

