2 STUDY SUMMARY

2.1 Protocol Summary Table

Protocol Title & Number	Exploratory trial to improve postextubation management for patients at risk for extubation failure IRB# 1332767
Study Short Title	GMC – [name] – Postextubation Management Pilot
Research Method	Prospective Interventional
Therapeutic Area	Pulmonary/Critical Care
Department	Intensive Care Unit, Critical Care Unit, 4 East
Study Description	This is an exploratory study designed to gather baseline information to determine the effectiveness of a standardized postextubation management protocol in a subset of patients at risk for reintubation.
Primary Endpoints	
• Proportion of patients that require reintubation within 72 hours• Association between reintubation rates and patient demographics or characteristics
Secondary Endpoints	
• Length of stay (ICU and total)• Ventilator time• In-hospital mortality• In-hospital adverse event rate• 30-day readmission rate
Prospective Cohort Study Population ^a	This study will include up to 40 mechanically ventilated, adult patients considered at-risk for re-intubation. See Section 6.3 . for detailed inclusion criteria.
Intervention(s)	
• Early NIV via BiPAP• High Flow Nasal Cannula breaks from NIV• Wean after 24 hours
Duration	Intervention Duration – Approximately 24 hours Study Duration – 3 months Participant Duration- total hospital stay, estimated at 14.1 ± 16.9 days (American Association for the Surgery of Trauma, 2011).

^a Data for this study will be compared to a historical control cohort, comprising mechanically ventilated, high-risk patients who underwent standard of care postextubation management.

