6.3 Participant Identification Procedures and Eligibility Criteria

6.3.1 Historical Control Group:

Reintubation rates are tracked at the institutional level as part of quality assessments; a delegated member of the study team will utilize this patient list to generate a study-specific subset of high-risk patients who were mechanically ventilated between February and October 2019. This list will be screened for the inclusion/exclusion criteria below by a delegated member of the study team. The study statistician or designee will then use a random number generator to generate a final group of 80 patients that meet inclusion criteria.

Inclusion Criteria

1. Age ≥ 18 years
2. Chronic cardiac or pulmonary condition
 - o COPD, history of based on any documentation notes
 - o CHF, history of based on any documentation notes
 - o Positive fluid balance, defined as a positive number when calculating fluid input minus fluid output over the approximate 24-hour-period prior to extubation
3. Documented modified RSBI between 58-105 on the day of extubation

Exclusion Criteria

1. Patients receiving comfort care or terminal extubation
2. Home ventilator, based on any documentation notes
3. Only primary extubations will be included (i.e., if the patient list query identifies multiple mechanical ventilations, only the primary encounter/event will be included)

6.3.2 Prospective Group:

An EMR-based report of all patients that have been on mechanical ventilation (MV) at Grant Medical Center for at least 24 hours will be generated daily (Monday through Friday), per standard procedure. Eligibility determination for this cohort will be conducted by a delegated member of the study team across two time points: pre-screening to determine eligibility to approach for consent, and eligibility on the day of extubation to determine enrollment eligibility (Appendix A). Only patients meeting all required eligibility criteria above will be enrolled to the study; any PHI collected for patients that are not subsequently enrolled will be destroyed after non-eligibility determination.

Pre-Screening Criteria:

1. No home ventilator, based on any documentation notes
2. Not scheduled for terminal extubation/comfort care
3. Has not had a failed extubation during the current hospital stay
4. Has not previously participated in the current trial

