5. Any other reason, at the discretion of the study team/clinical care staff, that should preclude the LARs being approached. These include, but are not limited to, facial trauma or other severe injuries that make extubation unlikely or that would make BiPAP contraindicated. Because patients will be screened daily, it is possible that a patient that fails pre-screening earlier in the stay may be eligible for enrollment later in their stay. This is okay.

Day of Extubation Criteria

1. Patient/LAR provided informed consent
2. Documented high-risk factors of interest (CHF, COPD, and/or positive fluid balance) as defined for the historical control cohort
3. The modified RSBI must be between 58-105
4. Patient must successfully complete spontaneous breathing trial and be determined eligible for extubation
5. Patient must not have extubated themselves
6. The patient must have no other contraindication that would preclude the postextubation protocol (e.g., facial trauma, tracheotomy, or any other reason that would preclude use of BiPAP or HFNC)
7. The patient must not be undergoing terminal extubation or placed on comfort care

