7.1.2 Secondary Statistical Analysis Methods

Total hospital length of stay, ICU length of stay, ventilator time, in hours, will be compared between groups using Wilcoxon rank sum tests, as the durations are expected to be markedly non-normally distributed and skewed.

In-hospital mortality and 30-day readmission rates will be compared between the groups using a chi-square test, or Fisher's exact test if the data in the 2x2 contingency table have cells with expected frequency of $n < 5$.

All secondary analyses will be completed on the ITT population.

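### The 72-hour reintubation outcome has no rule for death or comfort care without reintubation, and the control group's comfort-care exclusion has no time point

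*Combined protocol and SAP*

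**What the plan says.** **Outcome.** The protocol summary table (2.1) gives the primary endpoint as "Proportion of patients that require reintubation within 72 hours". Section 7.1.1 analyses it by logistic regression: "The primary analysis is comparison of the groups on reintubation rates within 72 hours on the ITT population". The further time windows are coded "Re-intubation required (no/yes". No section of the analysis plan says how to classify a patient who dies or moves to comfort care before any reintubation.

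**Death.** Mortality appears only as a secondary endpoint, for the whole hospital stay and without adjustment (7.1.2): "In-hospital mortality and 30-day readmission rates will be compared between the groups using a chi-square test", with Fisher's exact test for sparse tables.

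**Exclusions.** Section 6.3.1 excludes from the controls "Patients receiving comfort care or terminal extubation", with no time attached. Controls come from an existing list of patients "who were mechanically ventilated between February and October 2019". The list exists because "Reintubation rates are tracked at the institutional level as part of quality assessments". In section 6.3.2 the matching prospective criterion stands under the day-of-extubation criteria: "The patient must not be undergoing terminal extubation or placed on comfort care". A similar check is made at pre-screening. Under section 6.6, once the study protocol has been ordered and started, the patient is analysed whether or not it was completed.

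**The concern.** There are two separate gaps.

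First, death and a move to comfort care both prevent reintubation from being observed. With a no/yes outcome and everyone retained, a patient who deteriorates and is not reintubated falls into the same category as one who breathes unaided. If such events are more frequent in one group, that group's reintubation rate looks better than its course warrants, and no planned analysis links these events to the 72-hour outcome.

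Second, a control's later move to comfort care is visible to whoever screens the completed chart, and an exclusion without a date could be applied to it. A prospective patient with the same course cannot be removed. The two groups would then be defined by different rules, one of which depends on what happened after extubation.

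The study is meant to supply preliminary data for a randomized trial (3.1), so a shift in the estimated difference matters even where no test reaches significance.

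**Working it through.** The plan gives no event rates for death or comfort care, no target effect and no power calculation, so there is no figure to reproduce. What follows is sensitivity arithmetic.

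**Inputs from the documents.** 40 prospective patients and up to 80 controls (section 5). Reintubation rates r of 19% and 23% (the NIV and HFNC arms of the trial cited in 3.2), and 35% (the lower end of the 35% to 67% range in 3.2 for older patients with severe chronic disease, a narrower group than the one eligible here).

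**Assumed inputs.** c, the share of all controls who move to comfort care without reintubation: 2% to 15%. q, the share of reintubated controls who later move to comfort care: 10% to 30%.

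**Step 1: weight of one patient.** 1/40 = 2.5 points in the prospective group; 1/80 = 1.25 points in the controls.

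**Step 2: deaths.** Section 6.3.1 does not exclude deaths, so they are handled alike in both groups. Let the reintubation rates be p1 and p0, and the rates of death without reintubation d1 and d0. The composite difference is (p1 + d1) − (p0 + d0) = (p1 − p0) + (d1 − d0). If d1 = d0 the difference is unchanged; it moves only by d1 − d0. The odds ratio moves a little even at equal rates. For 19% v 23% it is (0.19/0.81)/(0.23/0.77) = 0.79. Adding an assumed 5% to both gives (0.24/0.76)/(0.28/0.72) = 0.81.

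**Step 3: hindsight removal of non-reintubated controls.** The true risk r is the same in both groups. The observed control rate becomes r/(1 − c).

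| c | r = 19% | r = 23% | r = 35% |
|---|---|---|---|
| 2% | 19.4% (+0.4) | 23.5% (+0.5) | 35.7% (+0.7) |
| 5% | 20.0% (+1.0) | 24.2% (+1.2) | 36.8% (+1.8) |
| 10% | 21.1% (+2.1) | 25.6% (+2.6) | 38.9% (+3.9) |
| 15% | 22.4% (+3.4) | 27.1% (+4.1) | 41.2% (+6.2) |

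The control rate rises, which favours the intervention. The shift is rc/(1 − c), so it grows in proportion to r.

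**Step 4: hindsight removal of reintubated controls.** The observed control rate becomes r(1 − q)/(1 − rq).

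| q | r = 19% | r = 23% | r = 35% |
|---|---|---|---|
| 10% | 17.4% (−1.6) | 21.2% (−1.8) | 32.6% (−2.4) |
| 20% | 15.8% (−3.2) | 19.3% (−3.7) | 30.1% (−4.9) |
| 30% | 14.1% (−4.9) | 17.3% (−5.7) | 27.4% (−7.6) |

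The control rate falls, which works against the intervention.

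**Step 5: both at once.** The rate is r(1 − q)/(1 − c − rq). With r = 35%, q = 10% and c = 6.5% it is 0.315/0.900 = 35.0%: the two effects cancel. The net sign cannot be known in advance.

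For scale, the two arms of the cited trial differ by 23 − 19 = 4 points.

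**The case against.** **The control exclusion most naturally means status at extubation.** It is worded in the present tense and paired with terminal extubation, which exists only at that event. Controls must have had a planned extubation (section 5), and their breathing index is taken that same day. A reader might infer that controls will be removed for later comfort care. The documents do not say so; they only fail to rule it out. This stands, and it makes the second gap one of missing wording.

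**Coding as 'no' is an inference.** The endpoint speaks of patients who require reintubation, which could mean needed or performed, and the data collection forms (Appendices A, F and G) are not in the text available. This stands too. But if neither the plan nor the forms settle it, the choice falls to the person abstracting the chart.

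**Deaths would not go unseen.** In-hospital mortality is compared, adverse events are tabulated by group (7.1.3), and a monitoring board reviews the prospective patients about monthly (8.2). This helps in part. None of these isolates the first 72 hours or ties death to the primary outcome. The mortality comparison also uses the same controls, so a hindsight exclusion could remove control deaths from it.

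**A stronger reading is tempting: that an apparent benefit could consist wholly of uncounted failures.** Such tables can be built. Suppose true failure is 35% in both groups (28/80 and 14/40) and all control failures are reintubations. If 2, 4 or 6 of the 14 prospective failures are deaths or comfort-care moves, the odds ratio for reintubation reads 0.80, 0.62 or 0.46 (chi-square p 0.58, 0.27, 0.09). This requires such events in one group and none in the other. Nothing in the documents supports that, and none of the tables reaches 0.05.

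**Conclusion.** The point holds as two modest gaps with a cheap remedy.

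- Death or a move to comfort care within 72 hours without reintubation would, as the outcome is written, be coded as a success, and no planned analysis shows how often that happens. Deaths distort the difference only to the extent that their rates differ between the groups.
- The control exclusion lacks the time point that its prospective counterpart has. If it were applied to later comfort care, the control rate would shift up by about 0.4 to 6 points or down by about 1.6 to 7.6 points, depending on which controls are removed.

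These ranges rest entirely on the assumed rates and on true reintubation risks of 19% to 35%. At a 2% comfort-care rate the upward shift is below 1 point. A reader might infer a bias in favour of the intervention; the documents fix neither its direction nor its presence. In an exploratory, non-randomized pilot this does not undermine the design, but the wording should be settled before controls are screened and data analysed.

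**What to change.** 1. Keep 72-hour reintubation as the primary outcome, and state how a patient who dies or moves to comfort care first is coded in it.
2. In section 6.3.1, state that the comfort-care and terminal-extubation exclusion is judged as of the extubation decision, from chart entries up to that time. Later events then play no part in selecting controls.
3. In section 7.1.1, add one prespecified supportive analysis of reintubation, death or move to comfort care within 72 hours, on ITT with the same logistic model. Comfort care has to be in the composite: a version with reintubation and death alone would still count a comfort-care patient alive at 72 hours as a success.
4. Report by group the number reintubated, the number who died without reintubation and the number who moved to comfort care without reintubation, all within 72 hours.

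The cost is one clarified criterion, one more model and a table row, with one more result to report. These events should be recorded in the chart, but the collection forms should be checked for the date and time of death and of any move to comfort care in both groups.

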3.2 Background

Intensive Care Unit (ICU) patients that are on mechanical ventilation (MV) are assessed regularly to determine whether they will be able to successfully breathe on their own if removed from the ventilator. This determination is important, as keeping patients on the ventilator longer than necessary can result in lung injury, infections, and increased length of stay (Zein et al., 2016; Karthika et al., 2016). Conversely, removing a patient from the ventilator too soon, when the patient cannot breathe unsupported, can result in multiple complications that require the patient to be placed back on the ventilator and may increase morbidity and mortality (Karthika et al., 2016).

Predicting whether or not a patient can be successfully liberated from mechanical ventilation is challenging, and approximately 12-14% of patients who undergo planned extubation require reintubation within 48-72 hours (Thille et al., 2013). Several risk factors have been associated with reintubation, including a weak cough and frequent suctioning (Esteban et al., 2002), rapid shallow breathing index >58 breaths/min/L, positive fluid balance during the 24 hours preceding extubation, and pneumonia as the reason for initial intubation (Frutos-Vivar et al., 2006). Patients who are ≥ 65 years of age with severe chronic cardiac or respiratory disease appear to be at particularly high risk for extubation failure, with reintubation rates ranging from 35% to 67% (Thille et al., 2013; Robiquet et al., 2006). Given the subsequent extubation failure in a high percentage of patients deemed appropriate for extubation, a number of studies have been conducted to determine whether postextubation management can be optimized in order to reduce the likelihood that a patient will need to be reintubated.

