4 SPECIFIC AIMS

The purpose of this study is to establish baseline data regarding the institutional reintubation rate in a specific, high-risk patient population of interest and to determine the preliminary effectiveness of a standardized intermittent NIV/HFNC protocol in patients considered high risk for reintubation. This is a prospective, non-randomized exploratory trial with the following specific aim(s):

Aim 1. Compare reintubation rates (within 72 hours) between patients that undergo a standardized, intermittent NIV/HFNC protocol and a historical control cohort.

Aim 2. Determine whether reintubation rates differ as a function of age, gender, co-morbidity, reason for intubation, service line/operative status, or modified RSBI.

Secondary aims include calculating length of stay (ICU and total hospital), total ventilator time, in-hospital mortality rate, adverse event rates, and 30-day readmission rate. The overall demographics of the interventional group will also be compared to the historical control cohort.

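### The primary model adjusts only for baseline factors that reach p<=0.05; at 40 v 80 moderate imbalances in prognostic factors often stay out, so the Aim 1 odds ratio can keep part of the confounding

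*Combined protocol and SAP*

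**What the plan says.** Section 7.1.1 expects the groups to differ because the study is not randomised, and gives this as the reason for logistic regression. The primary analysis is 72-hour reintubation in the ITT population, adjusted by "including any statistically significant demographic and baseline characteristics as covariates in the logistic regression model". Section 7.1 supplies the tests (t or Wilcoxon, chi-square or Fisher) and the threshold: "Results will be considered statistically significant if the p-value is less than or equal to 0.05".

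No covariate is fixed in advance for Aim 1. The plan has no propensity score, matching, weighting or sensitivity analysis. Section 6.1 says that the oxygen support given to controls will be recorded so that later analyses can allow for it, but that is care after extubation and not a baseline covariate.

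Elsewhere the protocol names factors that it regards as prognostic. Section 3.2 lists "rapid shallow breathing index >58 breaths/min/L, positive fluid balance during the 24 hours preceding extubation, and pneumonia as the reason for initial intubation", and describes patients aged 65 or over with severe chronic cardiac or respiratory disease as at particularly high risk. Aim 2 is to "Determine whether reintubation rates differ as a function of age, gender, co-morbidity, reason for intubation, service line/operative status, or modified RSBI". Neither list is carried into the Aim 1 model.

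**The concern.** A baseline factor confounds the comparison to the extent that it is both unbalanced and prognostic. A between-group p-value takes no account of prognosis, and it mixes the size of the imbalance with the sample size. Under the rule a prognostic factor is dropped at p=0.06, while a factor unrelated to reintubation enters at p=0.04.

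This rule is the only confounding control in the primary analysis. Section 3.1 says that the results will be used to plan a randomised trial. What is at stake is therefore how far the preliminary odds ratio can be interpreted, not a confirmatory decision.

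**Working it through.** The documents state no power or detectable difference, so there is no figure of the plan's own to reproduce.

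**Inputs.** Groups of 40 and 80 (section 5; both are upper limits in section 6.2). Threshold p<=0.05 (section 7.1). Two-sided tests and equal SDs are assumed, because the plan states neither.

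**1. Chance that a continuous factor enters.**
- Standard error of a standardised difference: sqrt(1/40 + 1/80) = 0.1936.
- Observed difference needed for entry: 1.96 x 0.1936 = 0.380 SD, or 1.980 x 0.1936 = 0.383 SD with the t value on 118 df.
- Power from the noncentral t, with noncentrality = true imbalance / 0.1936:

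| True imbalance (SD) | Noncentrality | Enters | Left out |
|---|---|---|---|
| 0.2 | 1.03 | 18% | 82% |
| 0.3 | 1.55 | 34% | 66% |
| 0.4 | 2.07 | 54% | 46% |
| 0.5 | 2.58 | 73% | 27% |
| 0.6 | 3.10 | 87% | 13% |

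Entry passes 50% at about 0.38 SD. Smaller cohorts raise the threshold: 0.42 SD at 30 v 80.

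**2. Chance that a binary factor enters.** All 2x2 tables at 40 v 80 were enumerated, with the plan's switch from chi-square to Fisher when an expected count is below 5. Intervention v control: 15% v 25% gives 22.7%; 30% v 40% gives 18.5%; 35% v 50% gives 33.3%. A 10-point gap in, say, CHF would usually go unadjusted.

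**3. Effect on the odds ratio.** Confounder strength and imbalance are not in the documents, so this step rests on assumptions. Simulation used 2,000 replicates per setting, Firth logistic regression throughout and a true odds ratio of 1.00. Assumed outcome odds ratios: age and RSBI 1.5 per SD, CHF 2.0, COPD 1.5, positive fluid balance 1.25. Nine imbalance scenarios were run. Three bear most on the point (median odds ratio under the plan's rule):

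| Scenario | About 14 events | About 26 | About 40 |
|---|---|---|---|
| Five factors lower in the intervention group (0.3 SD or 8 points) | 0.85 | 0.88 | 0.86 |
| Mixed signs | 0.99 | 0.96 | 0.98 |
| No imbalance | 1.04 | 1.01 | 0.96 |

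Across all nine scenarios at 14 to 40 events, the rule gives medians of 0.81 to 1.04. Forcing the five factors and keeping the rule for the rest gives 0.93 to 1.02.

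A separate check used one confounder, higher in the intervention group by 0.2 to 0.38 SD, with outcome odds ratios of 1.5 to 2.5 per SD. The geometric-mean odds ratio was 1.03 to 1.10 under the rule, 0.95 to 1.00 with the factor always in, and 1.07 to 1.34 with no adjustment. The rule therefore removes part of the confounding and leaves part.

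**4. Size against sampling error.** If the 23% and 19% quoted in section 3.2 applied to controls and intervention, events would be 0.23 x 80 + 0.19 x 40 = 18.4 + 7.6 = 26. The crude SE of the log odds ratio is sqrt(1/7.6 + 1/32.4 + 1/18.4 + 1/61.6) = 0.48. The bias at 26 events is ln(0.88) = -0.13, and 0.13/0.48 = 0.27, about a quarter of one SE.

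**The case against.** The best defence is that the rule is prespecified, does not look at the outcome, and catches large imbalances (87% at 0.6 SD). In the simulations, forced covariates did not improve overall accuracy: RMSE of the log odds ratio ran from 0.02 lower to 0.05 higher with the five factors forced. Coverage of the 95% interval was 94-96% both under the rule and with a longer forced list. The study is exploratory. All of this stands and limits the priority.

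Shared eligibility also helps in part. Both cohorts need "Documented modified RSBI between 58-105 on the day of extubation", so RSBI above 58 is essentially constant by design and cannot serve as an example of an omitted confounder. RSBI can still vary between 58 and 105, but whether it predicts reintubation in that range is a question for Aim 2. For the conditions, the prospective group needs "Documented high-risk factors of interest (CHF, COPD, and/or positive fluid balance) as defined for the historical control cohort". Any one suffices, so the mix of conditions can differ between cohorts.

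Three stronger readings are tempting and are not supported:
- A reader might infer that the Aim 1 estimate will favour the intervention. Nothing in the documents shows that the named factors lean one way. The direction in each simulation was an input.
- A reader might take the rule as certainly blind to prognosis. Section 7.1.1 does not say what the characteristics must be significant for. The between-group reading fits the sentence and section 7.1 best, but if significance in the outcome model were meant, the entry percentages above would not apply.
- A reader might infer that covariates are selected afresh in the per-protocol set, because section 7.1 will "compare groups on all the demographics and baseline characteristics, for the intention to treat (ITT) and per protocol (PP) populations". Section 7.1.1 does not say so, and it lists per-protocol repeats only for the separate time windows. The 72-hour primary analysis is not affected.

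**Conclusion.** The concern holds in a limited form. On the natural reading, the only confounding control for Aim 1 leaves out imbalances below about 0.38 SD more often than not, including imbalances in positive fluid balance, in age and chronic cardiac or respiratory disease, and in pneumonia as the reason for intubation. The entry percentages follow from the planned sizes and threshold, assuming two-sided tests and equal SDs.

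The consequence is conditional. Only if several prognostic factors are moderately unbalanced in the same direction does the odds ratio move to about 0.85-0.88 from a true 1.00, and that figure depends on assumed strengths and imbalances. The documents give neither the size nor the direction. Priority is low to moderate.

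**What to change.** In section 7.1.1, replace the selection sentence with wording to this effect:
- The primary model includes treatment group and, whatever their baseline p-values, age, modified RSBI (continuous, as an Aim 2 factor), CHF, COPD and positive fluid balance, the three conditions as separate terms.
- Any other baseline characteristic that differs between groups at p<=0.05 in ITT may be added, including reason for intubation if it is recorded in both groups. This also settles what significance refers to.
- The model is fitted with Firth penalisation, and the unadjusted and adjusted odds ratios are reported with 95% CIs.

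Penalisation is needed because events are few: 26 events over six terms (treatment and five covariates) is 26/6 = 4.3 per parameter.

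**Cost.** The change is to SAP wording. RSBI, CHF, COPD and fluid balance are eligibility items in both cohorts, and age is needed for eligibility or Aim 2. The data collection tools (Appendices A and F) are not shown, so recording in both cohorts should be confirmed. The list should be fixed before the comparative analysis starts, since section 6.3.1 draws controls from a list on which reintubation is already tracked. The statistical price is an SD of the log odds ratio about 4-8% higher, with RMSE about the same or slightly higher. The gain is lower bias when the named factors lean one way, not better overall accuracy.
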